6.3. Other Endpoints

6.3.1. PK Endpoints

Blood samples for PK analysis of PF-05208763 will be taken according to the Schedule of Activities given in the protocol.

The following PK parameters will be calculated for PF-05208763 (if possible) from the concentration-time data using standard noncompartmental methods:

Table 2. PK Parameters

PK Parameter	Analysis Scale	PF-05208763
AUC _{inf} *	ln	A, D
AUC _{last}	ln	A, D
C _{max}	ln	A, D
T _{max}	R	D
t _{1/2} *	R	D
CL/F*	ln	D
V _z /F*	ln	D

Key: A=analyzed using statistical model, D=displayed with descriptive statistics,
 ln=natural-log transformed, R=raw (untransformed), *=if data permits.

6.3.2. PD Endpoints

None.

6.4. Covariates

None.

7. HANDLING OF MISSING VALUES

For the analysis of safety endpoints, the sponsor data standard rules for imputation will be applied.

7.1. Concentrations Below the Limit of Quantification

In all data presentations (except listings), concentrations below the limit of quantification (BLQ) will be set to zero. (In listings BLQ values will be reported as “<LLQ”, where LLQ will be replaced with the value for the lower limit of quantification.)

7.2. Deviations, Missing Concentrations and Anomalous Values

In summary tables and plots of median profiles, statistics will be calculated having set concentrations to missing if 1 of the following cases is true:

1. A concentration has been collected as ND (ie, not done) or NS (ie, no sample).
2. A deviation in sampling time is of sufficient concern or a concentration has been flagged anomalous by the pharmacokineticist.

Note that summary statistics will not be presented at a particular time point if more than 50% of the data are missing.

7.3. Pharmacokinetic Parameters

Actual PK sampling times will be used in the derivation of PK parameters.

If a PK parameter cannot be derived from a subject's concentration data, the parameter will be coded as NC (ie, not calculated). (Note that NC values will not be generated beyond the day that a subject discontinues).

In summary tables, statistics will be calculated by setting NC values to missing; and statistics will be presented for a particular treatment with ≥ 3 evaluable measurements. For statistical analyses (ie, analysis of variance), PK parameters coded as NC will also be set to missing; and analyses will not be performed for a particular parameter if more than 50% of the data are NC.

If an individual subject has a known biased estimate of a PK parameter (due for example to an unexpected event such as vomiting before all the compound is adequately absorbed in the body), this will be footnoted in summary tables and will not be included in the calculation of summary statistics or statistical analyses.

8. STATISTICAL METHODOLOGY AND STATISTICAL ANALYSES

8.1. Statistical Methods

Precision of the estimate of PK parameters will be determined by constructing 90% confidence intervals around the estimated difference between the Test and Reference treatments using a mixed effects model based on natural log transformed data. The mixed effects model will be implemented using SAS Proc Mixed, with REML estimation method and Kenward-Roger degrees of freedom algorithm.

8.2. Statistical Analyses

Natural logarithm-transformed AUC_{inf} , AUC_{last} and C_{max} will be analyzed using a mixed effect model with sequence, period and treatment as fixed effects and participant within sequence as a random effect. Estimates of the adjusted mean differences (Test-Reference) and corresponding 90% CIs will be obtained from the model. The adjusted mean differences and 90% CIs for the differences will be exponentiated to provide estimates of the ratio of adjusted geometric means (Test/Reference) and 90% CIs for the ratios.

The following 2 comparisons will be performed:

- *Treatment B (Test) vs Treatment A (Reference).*
- *Treatment A (Test) vs Treatment C (Reference).*

Residuals from the model will be examined for normality and the presence of outliers via visual inspection of plots of residuals vs predicted values and normal probability plots of residuals but these will not be included in the clinical study report. If there are major deviations from normality or outliers, then the effect of these on the conclusions will be investigated through alternative transformations and/or analyses excluding outliers. Justification for any alternative to the planned analysis will be given in the report of the study.

Table 3. PK Parameters to be Summarized Descriptively by Treatment

Parameter	Summary Statistics
AUC_{inf}^* , AUC_{last} , C_{max}	N, arithmetic mean, median, cv%, standard deviation, minimum, maximum, geometric mean and geometric cv%.
T_{max}	N, median, minimum, maximum.
$t_{1/2}^*$	N, arithmetic mean, median, cv%, standard deviation, minimum, maximum.
CL/F^*	N, arithmetic mean, median, cv%, standard deviation, minimum, maximum, geometric mean and geometric cv%.
Vz/F^*	N, arithmetic mean, median, cv%, standard deviation, minimum, maximum, geometric mean and geometric cv%.

*: if data permit.

For AUC_{inf} , AUC_{last} and C_{max} , a listing of the individual participant ratios (Test-Reference) will be provided for the 2 comparisons described above. Individual participant bosutinib PK parameters for AUC_{inf} , AUC_{last} and C_{max} will be plotted by treatment and overlaid with geometric mean. Bosutinib plasma concentrations will be listed and summarized descriptively by PK sampling time and treatment. Individual participant and median profiles of the concentration-time data will be plotted by treatment. For summary statistics and median plots by sampling time, the nominal PK sampling time will be used; for individual participant plots by time, the actual PK sampling time will be used.

Supporting data from the estimation of $t_{1/2}$ and AUC_{inf} will be listed by treatment: terminal phase rate constant (k_{el}); goodness of fit statistic from the log-linear regression (r^2); the percent of AUC_{inf} based on extrapolation ($AUC_{extrap\%}$); and the first, last, and number of time points used in the estimation of k_{el} . This data may be included in the clinical study report.

Presentations for PF-05208763 concentrations will include:

- A listing of all concentrations sorted by subject ID, period and nominal time postdose. The concentration listing will also include the actual times. Deviations from the nominal time will be given in a separate listing.

- A summary of concentrations by treatment and nominal time postdose, where the set of statistics will include n, mean, median, standard deviation, coefficient of variation (cv), minimum, maximum and the number of concentrations above the lower limit of quantification.
- Median concentrations time plots (on both linear and semi-log scales) against nominal time postdose by treatment (all treatments on the same plot per scale, based on the summary of concentrations by treatment and time postdose).
- Mean concentrations time plots (on both linear and semi-log scales) against nominal time postdose by treatment (all treatments on the same plot per scale, based on the summary of concentrations by treatment and time postdose).
- Individual concentration time plots by treatment (on both linear and semi-log scales) against actual time postdose (there will be separate spaghetti plots for each treatment per scale).
- Individual concentration time plots by subject (on both linear and semi-log scales) against actual time postdose [there will be separate plots for each subject (containing all treatments) per scale].

If an individual participant has a known cause for biased estimate of a PK parameter (due for example to an event such as vomiting before all of the drug is absorbed in the body), this will be footnoted in summary tables and will not be included in the calculation of summary statistics or statistical analyses. Participants who vomited at or before 2 times of median T_{max} after drug administration may be excluded from PK analysis.

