Natural logarithm-transformed bosutinib AUC_{inf} , AUC_{last} and C_{max} will be analyzed using a mixed effect model with sequence, period and treatment as fixed effects and participant within sequence as a random effect. Estimates of the adjusted mean differences (Test-Reference) and corresponding 90% CIs will be obtained from the model. The adjusted mean differences and 90% CIs for the differences will be exponentiated to provide estimates of the ratio of adjusted geometric means (Test/Reference) and 90% CIs for the ratios.

The following 2 comparisons will be performed:

- Treatment B (Test) vs Treatment A (Reference)
- Treatment A (Test) vs Treatment C (Reference)

The plasma PK parameters AUC_{inf} , C_{max} , AUC_{last} , T_{max} , CL/F , V_z/F and $t_{1/2}$ of bosutinib will be summarized descriptively by treatment. For AUC_{inf} , AUC_{last} and C_{max} , a listing of the individual participant ratios (Test-Reference) will be provided for the 2 comparisons described above. Individual participant bosutinib PK parameters for AUC_{inf} , AUC_{last} and C_{max} will be plotted by treatment and overlaid with geometric mean. Bosutinib plasma concentrations will be listed and summarized descriptively by PK sampling time and treatment. Individual participant and median profiles of the concentration-time data will be plotted by treatment. For summary statistics and median plots by sampling time, the nominal PK sampling time will be used; for individual participant plots by time, the actual PK sampling time will be used.

AEs, ECG, BP, pulse rate, and safety laboratory data will be reviewed and summarized on an ongoing basis during the study to evaluate the safety of participants. Any clinical laboratory, ECG, BP, and pulse rate abnormalities of potential clinical concern will be described. Safety data will be presented in tabular and/or graphical format and summarized descriptively, where appropriate.

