4.2. Scientific Rationale for Study Design

The current study aims to determine the oral bioavailability of the age-appropriate 100 mg capsule relative to the 25 mg clinical capsules when orally administered under fed condition in healthy participants and also to characterize the effect of food on the plasma pharmacokinetics of bosutinib following administration of the proposed 100 mg commercial capsule.

The study is being designed as a crossover study to account for any period effects. Between each sequential dosing of bosutinib, a minimum of 14-day washout is proposed to minimize any residual bosutinib concentrations prior to start of the next period, as bosutinib has a plasma elimination $t_{1/2}$ of approximately 34 hours.

Bosutinib is currently labeled to be administered with food for improved tolerability. Therefore, the evaluation of relative bioavailability assessment in Treatments A and B will be conducted under fed condition using a high-fat, high-calorie meal^{2,3}.

Based on findings from animal studies and its mechanism of action, bosutinib can cause fetal harm when administered to a pregnant woman, therefore, females of child-bearing potential will be excluded from the study. In addition, the use of a highly effective method of contraception is required for male participants with female partners of child bearing potential (see [Appendix 4](#)).

Retained Research Samples will be collected and stored for further analyses which may, for example, provide greater understanding of the study intervention.

CCI

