9. STATISTICAL CONSIDERATIONS

Detailed methodology for summary and statistical analyses of the data collected in this study is outlined here and further detailed in a SAP, which will be maintained by the sponsor. The SAP may modify what is outlined in the protocol where appropriate; however, any major modifications of the primary endpoint definitions or their analyses will also be reflected in a protocol amendment.

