9.3. Statistical Analyses

The SAP will be developed and finalized prior to database lock before any analyses are performed and will describe the analyses and procedures for accounting for missing, unused, and spurious data. This section is a summary of the planned statistical analyses of the primary and secondary endpoints

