9.3.1. Pharmacokinetics Endpoint(s)

PK parameters for bosutinib following single dose administration will be derived from the concentration time profiles using non-compartmental methods as data permit. The various bosutinib PK parameters to be assessed in this study; their definition, and method of

determination are outlined in Table 5. In all cases, actual PK sampling times will be used in the derivation of PK parameters.

Table 5. Definitions of PK Parameters

Parameter	Definition	Method of Determination
AUC _{last}	Area under the plasma concentration-time profile from time zero to the time of the last quantifiable concentration (C _{last})	Linear-log trapezoidal method
AUC _{inf} ^a	Area under the plasma concentration-time curve from time zero extrapolated to infinite time	AUC _{last} + (C _{last} */k _{el}) where C _{last} * is the predicted plasma concentration at the last quantifiable time point estimated from the log-linear regression analysis and k _{el} is the terminal phase rate constant calculated by a linear regression through at least 3 data points in the terminal phase of the log-linear concentration-time curve.
C _{max}	Maximum plasma concentration	Observed directly from the data
T _{max}	Time for C _{max}	Observed directly from the data as time of first occurrence
t _{1/2} ^a	Terminal elimination half-life	Log _e (2)/k _{el} , only those data points judged to describe the terminal log-linear decline will be used in the regression.
CL/F ^a	Apparent clearance after oral dose	Dose/AUC _{inf} after oral dose
V _z /F ^a	Apparent volume of distribution after oral dose	Dose/(AUC _{inf} *k _{el}) after oral dose

a. As data permits.

Natural logarithm-transformed AUC_{inf}, AUC_{last} and C_{max} will be analyzed using a mixed effect model with sequence, period and treatment as fixed effects and participant within sequence as a random effect. Estimates of the adjusted mean differences (Test-Reference) and corresponding 90% CIs will be obtained from the model. The adjusted mean differences and 90% CIs for the differences will be exponentiated to provide estimates of the ratio of adjusted geometric means (Test/Reference) and 90% CIs for the ratios.

The following 2 comparisons will be performed:

[figure not shown]
- Treatment B (Test) vs Treatment A (Reference)
- Treatment A (Test) vs Treatment C (Reference)

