10. APPENDICES

Appendix 1. SAS CODE FOR ANALYSES

An example of the PROC MIXED code is provided below:

```
proc mixed data=tab.pk;
  class seq period trt subject;
  model l&var=seq period trt/ ddfm=KR;
  random subject(seq) /subject=subject(seq);
  lsmeans trt;
  estimate 'B vs A' trt -1 1 0 /cl alpha=0.1;
  estimate 'A vs C' trt 1 0 -1 /cl alpha=0.1;
  ods 'Estimates' out=est&var;
  ods 'lsmeans' out=ls&var;
  ods 'covparms' out=cov&var;
  ods 'tests3' out=tst&var;
run;
```

/* Letter assignments for treatments (trt) within the estimate statement above are as follows;

A = Treatment A: 1 × 100 mg capsule under fed condition;
B = Treatment B: 4 × 25 mg capsules under fed condition;
C = Treatment C: 1 × 100 mg capsule under fasted condition;
*/;

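### Treatment C is given only in Period 3, and Period 3 holds only Treatment C, so the planned model cannot estimate the food effect (A vs C)

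*SAP*

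**What the plan says.** Protocol Table 3 and SAP Table 1 give the same design, with 7 participants per sequence:

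| Sequence | Period 1 | Period 2 | Period 3 |
|---|---|---|---|
| 1 | A | B | C |
| 2 | B | A | C |
| 3 | A | B | none |
| 4 | B | A | none |

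A is one 100 mg capsule fed, B is four 25 mg capsules fed, and C is one 100 mg capsule fasted. The food effect, A vs C, is one of two primary objectives.

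SAP 8.2 states that the log-transformed parameters will be "analyzed using a mixed effect model with sequence, period and treatment as fixed effects and participant within sequence as a random effect". The protocol synopsis and Protocol 9.3.1 give the same model. The code in SAP Appendix 1 carries it out with "model l&var=seq period trt/ ddfm=KR", requests adjusted means for every treatment, and asks for the food effect with "estimate 'A vs C' trt 1 0 -1 /cl alpha=0.1".

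Protocol 4.2 gives the reason for the design: "The study is being designed as a crossover study to account for any period effects". SAP 8.2 allows a different analysis only for marked non-normality or outliers.

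**The concern.** A model that contains both period and treatment can separate them only if some treatment other than C is given in Period 3, or C is given in some other period. Neither happens here. The comparison of fed with fasted dosing is also a comparison of Periods 1 and 2 with Period 3, and the planned model has no information to divide the two.

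Two things are at stake. First, the planned estimate and interval for a primary objective would come back as non-estimable. Second, if this is first noticed when the code is run, the replacement model will be chosen with the data in hand, although Protocol 9.3 promises that "The SAP will be developed and finalized prior to database lock before any analyses are performed".

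**Working it through.** **Inputs.** The sequences and 7 participants per sequence come from Protocol Table 3 and SAP Table 1. That gives 14 × 3 + 14 × 2 = 70 observations. The within-subject SDs on the log scale, 0.1560 (AUCinf) and 0.2373 (Cmax), come from Protocol 9.5.

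**1. The plan's own precision figure.** Protocol 9.5 states half-widths of ±0.0786 and ±0.1196. They are reproduced by t(0.95, 26) × SD × √(2/28) × √(χ²(p, 26)/26) with p = 0.80. With p = 0.90, the probability named in the text, the result is 0.0832 and 0.1265; that mismatch is a separate matter. What counts here is that the figure uses all 28 participants, so it describes B vs A. Only 14 participants receive C, and no precision is given for A vs C.

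**2. Rank.** The fixed-effects matrix has 1 + 4 + 3 + 3 = 11 columns (intercept, sequences, periods, treatments). If period and treatment were separable, its rank would be 1 + 3 + 2 + 2 = 8. The Period 3 column equals the Treatment C column, and the rank is 7.

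**3. Estimability.** Add any amount δ to the Period 3 effect and subtract δ from the Treatment C effect. Every expected value in the design stays the same, so no data can determine δ. A quantity that changes with δ is not estimable.

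| Quantity | Change | Estimable |
|---|---|---|
| B − A | 0 | yes |
| A − C | +δ | no |
| B − C | +δ | no |
| Adjusted mean A or B (averaged over 3 periods) | +δ/3 | no |
| Adjusted mean C | δ/3 − δ = −2δ/3 | no |

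A numerical check on the 70 × 11 matrix agrees line by line. The random participant effect does not alter this. Removing sequence does not restore A − C; removing period does.

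**4. Precision of A vs C without period.** Two data sets are possible.

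- (i) A and C data from Sequences 1 and 2, 14 participants: SE = SD × √(2/14), with 28 − 14 − 1 = 13 df.
- (ii) All 70 observations: A − C is [(A + B)/2 − C], from 14 participants, plus (A − B)/2, from 28. SE = SD × √(1.5/14 + ¼ × 2/28) = SD × √0.125, with 70 − 28 − 2 = 40 df.

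| | SE, AUCinf | SE, Cmax | t(0.95) | Half-width, AUCinf | Half-width, Cmax |
|---|---|---|---|---|---|
| (i) | 0.0590 | 0.0897 | 1.771 | 0.104 | 0.159 |
| (ii) | 0.0552 | 0.0839 | 1.684 | 0.093 | 0.141 |

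For B vs A, SE = SD × √(2/28) = 0.0417 and 0.0634, with or without the period term. The half-widths in the table are expected values (t × SE). They carry no probability margin, so they are not comparable with the figures in Protocol 9.5.

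**5. What the estimate then contains.** In Sequences 1 and 2, A falls equally in Periods 1 and 2. Both (i) and (ii) therefore estimate the true A − C plus (Period 1 + Period 2)/2 minus Period 3. A Period 3 shift passes through one for one. A shift of +0.10 on the log scale multiplies the A/C ratio by exp(−0.10) = 0.905, a fall of 9.5%. The documents give no size for a period effect; 0.10 is only an illustration.

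**The case against.** The strongest reply is that the defect has little practical effect. The study only estimates, with no hypotheses or decision rules. A programmer who meets the non-estimable contrast would drop period. Carryover is also unlikely to matter: 14 days is 336 h, which is 336/34 = 9.9 half-lives at the mean and 336/55 = 6.1 at the top of the quoted range, leaving roughly 0.1% to 1.4%. Descriptive geometric means and individual A/C ratios are still planned.

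The carryover argument stands, but carryover is only one source of a period effect, and Protocol 4.2 itself claims to account for any such effect. The descriptive output also remains, but it is not the adjusted ratio with a 90% CI, and it carries the same Period 3 shift. Dropping period is the natural repair, yet no visible text provides for it, and it brings in an assumption that the plan does not declare.

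A fair point concerns the repair. B vs A is not broken, so a separate model for it is not strictly needed. One could keep a single model and constrain Period 3 to the average of Periods 1 and 2. That gives SE 0.0417 for B − A and 0.0552 for A − C in AUCinf, with 39 df. It is a valid alternative that rests on the same assumption. Using only A and B data lowers the df for B vs A from 39 to 26 and widens its expected AUCinf half-width from 0.0702 to 0.0711, about 1%. In return, the adjusted means for A and B no longer depend on anything in Period 3.

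**Conclusion.** The concern holds. Under the prespecified model, A vs C and the adjusted means for A, B and C are not estimable, so the model-based food-effect ratio and its 90% CI cannot be produced for any of the three parameters. This follows from the sequence table alone and needs no assumption about variances or the size of period effects. It presumes dosing as randomized; an accidental out-of-order dose could break the aliasing, but the contrast would then rest on that error.

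The B vs A bridging comparison is unaffected. The precision figures for the repaired analysis assume the SDs in Protocol 9.5 and no dropout. No reanalysis of this design can separate the food effect from a Period 3 effect; it can only state the assumption.

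**What to change.** Before database lock, replace the single model with two.

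1. **B vs A:** Treatment A and B data from Periods 1 and 2; sequence, period and treatment fixed; participant within sequence random (28 participants).
2. **A vs C:** sequence and treatment fixed; participant within sequence random; no period term. Name one data set in advance. I suggest A and C data from Sequences 1 and 2, a simple paired comparison in 14 participants. All 70 observations are a somewhat more precise alternative.

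Take the adjusted means from these models. In SAP Appendix 1, remove period from the A-vs-C MODEL statement. Use two-coefficient ESTIMATE statements for the two-treatment data sets (B vs A: -1 1; A vs C: 1 -1).

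State in the SAP and the report that A vs C assumes Period 3 does not differ from the average of Periods 1 and 2. Add that unequal dropout between Sequences 1 and 2 would also let a Period 1 vs 2 difference into the estimate. Qualify the sentence on period effects in Protocol 4.2.

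The synopsis and Protocol 9.3.1 need the same change. Protocol 9 says that "any major modifications of the primary endpoint definitions or their analyses will also be reflected in a protocol amendment", and I read a new model for a primary comparison as falling under that. The cost is text, code and an amendment, with no extra participants, doses or samples.

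Only if randomization has not started (the documents do not say), C could be placed in more than one period, for example A-B-C, B-C-A, A-B, B-A. The planned model then has rank 8 and estimates both contrasts with the same 28 participants and 70 doses. For AUCinf, SE(A − C) is 0.0590 and SE(B − A) rises from 0.0417 to 0.0442, about 6%. This needs an amendment and a new randomization schedule.
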